7.3.4 Visual Analog Scale

Acceptability outcomes will include a Visual Analogue Scale (VAS) of acceptability of the Cytosponge, TNE, and EGD. Also, the subject will be asked whether he/she would be willing to repeat the assay, and,

assuming similar accuracy between modalities, whether he/she would rather undergo surveillance by Cytosponge, TNE, or standard EGD with biopsies.

7.4 Follow-Up Phone Call

Subjects will be contacted approximately seven (7) days after successful administration of the device via phone or other IRB approved method. The following data will be collected from subjects during the follow-up phone call:

- Impact of Events Scale (IES)
 - Cohort A: IES for EGD and TNE only (IES data has been previously collected for Cytosponge in the prior study)
 - Cohort B: IES for EGD, TNE, and Cytosponge
- Procedure Preference and Acceptability Questionnaire
- Adverse event assessment
- Follow-Up Case Report Form (eCRF): This captures relevant information for questionnaire completion and assessment of adverse events.

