7.4.1 Impact of Events Scale

The Impact of Events Scale (IES) will be completed with the subject during the follow-up phone call and measures subjective distress related to the administered procedures. Primary assessment of acceptability will be via the Impact of Events Scale. This widely used scale was developed to assess the distress associated with a specific life event. It includes measures of both the intrusiveness of the event, and any avoidance responses by the subject in response to the event. IES has been used to measure acceptability of Cytosponge in prior studies.^{25,26} *In addition the previous study referenced here UNC IRB #13-2618, used the IES instrument and therefore we have utilized the same instrument in this protocol so the data is comparable.*

For Cohort A subjects, we plan to use existing IES data pertaining to Cytosponge which was collected seven (7) days after Cytosponge administration in the prior study. Since a period of time has passed since the patients in Cohort A underwent Cytosponge, using the already collected data will help minimize recall bias. Therefore, Cohort A subjects will only have IES collected for TNE procedure and EGD during this current proposed study.

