7.4.2 Procedure Preference and Acceptability Questionnaire

The procedure preference and acceptability questionnaire will be completed with the subject during the follow-up phone call. This assessment collects subject preference for the Cytosponge vs. traditional upper endoscopy vs. TNE, as well as willingness to undergo the procedure again.

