12.2 Procedure Preference and Acceptability Questionnaire

[figure not shown]
1. On a scale of 0-10, please rate your experience with the Cytosponge procedure:

2. On a scale of 0-10, please rate your experience with the transnasal endoscopic procedure (TNE):

3. On a scale of 0-10, please rate your experience with the traditional upper endoscopic procedure (EGD):

4. Would you be willing to repeat the Cytosponge procedure if your physician indicated it was medically necessary? Yes No

5. Would you be willing to repeat the transnasal procedure (TNE) if your physician indicated it was medically necessary? Yes No

6. Would you be willing to repeat the traditional upper endoscopic procedure (EGD) if your physician indicated it was medically necessary? Yes No

7. Which procedure would you prefer to undergo again if your physician indicated it was medically necessary? Traditional Upper Endoscopy (EGD) Cytosponge Transnasal Endoscopy (TNE)

8. What factors, if any, influenced your decision (select all that apply)?

Discomfort/Pain Time (needed for preparation) Cost Need for Sedation
 Other: Describe:

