12.3 Impact of Events Scale (IES)

Below is a list of comments made by people in connection with their [Cytosponge/TNE/EGD] screening test. Please check each item, indicating how frequently these comments were true for you during the **past seven (7) days**. If they did not occur during that time, please mark the 'not at all' column.

	Not at all	Rarely	Sometimes	Often
I thought about it when I did not mean to.				
I avoided letting myself get upset when I thought about it or was reminded of it.				
I tried to remove it from my memory.				
I had trouble falling asleep or staying asleep, because of pictures or thoughts about it that came into my mind.				
I had waves of strong feelings about it.				
I had dreams about it.				
I stayed away from reminders of it.				
I felt as if it wasn't happening to me, or wasn't real.				
I tried not to talk about it.				
Pictures about it popped into my mind.				
Other things kept making me think about it.				
I was aware that I still had a lot of feelings about it, but I didn't deal with them.				
I tried not to think about it.				
Any reminder brought back feelings about it.				

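### Question order is fixed by modality on the preference form and is unspecified and unrecorded for the IES; rotating and recording it is a cheap improvement

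*Combined protocol and SAP*

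**What the plan says.** **Contact.** Section 7.4 has subjects contacted about seven days after the procedure "via phone or other IRB approved method". Of the preference form, Section 7.4.2 says: "The procedure preference and acceptability questionnaire will be completed with the subject during the follow-up phone call".

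**IES.** Section 7.4 gives the content by cohort: "Cohort A: IES for EGD and TNE only (IES data has been previously collected for Cytosponge in the prior study"), and "Cohort B: IES for EGD, TNE, and Cytosponge". Section 7.4.1 names the two Cohort A modules the other way round: "Cohort A subjects will only have IES collected for TNE procedure and EGD during this current proposed study". Section 12.3 is a single 14-item template with the modality filled in: "Below is a list of comments made by people in connection with their [Cytosponge/TNE/EGD] screening test".

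**Preference form (12.2).** Items 1 to 3 are ratings and begin with Cytosponge: "1. On a scale of 0-10, please rate your experience with the Cytosponge procedure". TNE and EGD follow. Items 4 to 6, on willingness to repeat, keep that order. Item 7 asks "Which procedure would you prefer to undergo again if your physician indicated it was medically necessary" and offers EGD, Cytosponge, TNE.

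**Analysis.** Section 9.1 compares IES between modalities by Kruskal-Wallis and chi-square tests. Willingness to repeat and top preference are reported as proportions. Factors influencing preference are examined by bivariate and multinomial logistic regression. The two cohorts are analysed separately and together.

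Neither document part mentions rotating, counterbalancing or recording the order of questions.

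**The concern.** The study compares three modalities by putting near-identical questions to the same person. Answers to such questions can depend on position: respondents tire, repeat their previous answers, or favour the first or last option in a list, particularly when it is read aloud. If position and modality coincide for everyone, a position effect looks like a modality effect, and no later analysis can separate them.

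Willingness to repeat (secondary objective 2) and preferred modality (objective 3) are directly exposed, because the form fixes their order. Objective 4 is exposed as well, since item 7 supplies the preference it models. For the primary IES comparison, the difficulty is that nobody could tell afterwards whether order mattered. Procedure order is constrained by clinical workflow; question order is free to vary.

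**Working it through.** **1. Is the order fixed?** The places that name the modalities, side by side:

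| Place | Order shown | Fixes the order of asking? |
|---|---|---|
| 7.4, Cohort B IES | EGD, TNE, Cytosponge | No, a content list |
| 7.4, Cohort A IES | EGD, TNE | No, a content list |
| 7.4.1, Cohort A IES | TNE, EGD | No, a content list |
| 12.3, IES template | Cytosponge, TNE, EGD | No, a fill-in field |
| 12.2, items 1-3 and 4-6 | Cytosponge, TNE, EGD | Yes, printed |
| 12.2, item 7 | EGD, Cytosponge, TNE | Yes, printed |

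The order is fixed within each block of form 12.2. For the IES the listings disagree and none is an instruction. Staff may follow a habitual order, which would tie position to modality, or vary it without a record. The data would not show which.

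**2. Amount of repetition.** 14 items × 3 modules = 42 IES items in Cohort B; 14 × 2 = 28 in Cohort A.

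**3. The plan's own figure.** Inputs from Section 9.1: high-IES rates of 1% (EGD), 5% (Cytosponge) and 20% (TNE), correlation 0.3, 40 subjects, Fisher's exact test at 0.05, stated power 80%. A simulation of 40,000 trials, with correlated binary triplets from a Gaussian copula and an exact 3×2 test, gives 80.9% at latent correlation 0.3 and 80.4% at zero. The stated power reproduces. The 0.3 is read here as a latent correlation, because the largest Pearson correlation possible between a 1% and a 20% binary outcome is √[(0.01 × 0.80)/(0.99 × 0.20)] = 0.201.

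**4. Scale of an IES order effect (assumed).** The documents give no size. Assume 0.1 to 0.2 SD between first and last module, and borrow the 0.3 correlation for continuous scores.

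- SD of a paired difference = √[2(1 − 0.3)] = 1.183 SD.
- Detectable with 80% power = 2.88/√40 × 1.183 = 0.455 × 1.183 = 0.54 SD. Here 2.88 is the sum of the two-sided 5% and 80% power quantiles with a small-sample allowance.
- 0.1/0.54 = 19% and 0.2/0.54 = 37%.

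This is a paired yardstick, not the planned Kruskal-Wallis test. It takes a first-versus-last contrast in all 40 subjects, whereas a third module exists only in Cohort B.

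**5. Scale for the high/low test (assumed).** Suppose all three modalities truly have a 10% high-score rate, and the odds rise with position up to a given odds ratio (OR) for the third module, in the same order for all 40 subjects. With 20,000 trials per row at latent correlation 0.3:

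| OR, third module | Rates by position | Fisher rejection |
|---|---|---|
| 1 | 10%, 10%, 10% | 2.5% |
| 1.25 | 10%, 11.0%, 12.2% | 3.2% |
| 1.5 | 10%, 12.0%, 14.3% | 4.6% |
| 2 | 10%, 13.6%, 18.2% | 9.9% |

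Of these scenarios, only OR 2 takes rejection above the nominal 5%.

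**6. Scale for item 7 (assumed).** A shift of 5 to 10 points towards the first or last option is 0.05 × 40 = 2 to 0.10 × 40 = 4 subjects. For comparison, the 95% half-width of a proportion near one half is 1.96 × √(0.25/40) = 15 points.

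**The case against.** A reader might infer that the IES modules are put to every subject by phone in one printed order, so that the primary comparison is confounded beyond repair. The documents do not support that. Section 7.4 lists content, Sections 7.4.1 and 12.3 list other orders, and a method other than phone is allowed. Cohort A answers two modules, not three. By Section 5.1, Cohort A is the main recruitment route and Cohort B the fallback, so the 42-item call may apply to few subjects. All of this stands.

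A reader might also infer that question order spoils the Cohort A versus Cohort B comparison for Cytosponge. The context does differ: Cohort A's Cytosponge IES was answered in the earlier study, and Cohort B's at the same contact as the other modules. But the larger difference is the earlier study and time, which rotation cannot change, and Section 9.1 already plans separate cohort analyses and acknowledges carryover.

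Further points count against a high rating. No modality is favoured throughout form 12.2: EGD is last in items 1 to 6 and first in item 7. The 0-10 ratings are not named in any objective or analysis. Willingness and preference have no planned between-modality test. Every effect size above is assumed, and a shift of 2 to 4 subjects is smaller than the sampling error of a proportion at this sample size.

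These points limit the severity; they do not remove the concern. A smaller error that always runs in the same direction is still a bias, and separate cohort analyses leave a position effect within each cohort untouched.

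**Conclusion.** The point holds in two parts of different strength. On form 12.2, position is tied to modality within each block by the printed form, so any position effect on willingness or preference cannot be distinguished from a modality difference. For the primary IES, module order is unspecified, uncontrolled and unrecorded, so an order effect is possible and could not be checked; confounding is not established.

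The size is unknown. The figures of 19% to 37% of the detectable difference, and of 2 to 4 subjects on item 7, rest wholly on the assumed 0.1 to 0.2 SD and 5 to 10 points. In the high/low illustration only a large effect distorts the test materially. The Cytosponge, TNE, EGD procedure sequence in Cohort B is also tied to modality and would remain so. Low severity: worth changing because it is nearly free and cannot be recovered once the data are collected.

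**What to change.** In Sections 7.4 and 12.2:

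- Rotate the IES modules: EGD and TNE in Cohort A, all three in Cohort B.
- Rotate the modality order of the rating items, the willingness items and the item 7 options.
- Use a simple balanced rotation. Three cyclic orders are enough if Cohort B is small.
- Record the order used in one eCRF field.
- In Section 9.1, state that results will be shown by order descriptively.

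The cost is several versions of the existing forms and one extra field. Sample size, procedures and patient burden do not change. The limitation is that few subjects will fall in each order, so a formal test of order would have little power. The value lies in balancing order across modalities and being able to show that it was done. The fixed procedure order and the earlier collection of Cohort A's Cytosponge IES should still be reported as limitations.

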7.4.1 Impact of Events Scale

The Impact of Events Scale (IES) will be completed with the subject during the follow-up phone call and measures subjective distress related to the administered procedures. Primary assessment of acceptability will be via the Impact of Events Scale. This widely used scale was developed to assess the distress associated with a specific life event. It includes measures of both the intrusiveness of the event, and any avoidance responses by the subject in response to the event. IES has been used to measure acceptability of Cytosponge in prior studies.^{25,26} *In addition the previous study referenced here UNC IRB #13-2618, used the IES instrument and therefore we have utilized the same instrument in this protocol so the data is comparable.*

For Cohort A subjects, we plan to use existing IES data pertaining to Cytosponge which was collected seven (7) days after Cytosponge administration in the prior study. Since a period of time has passed since the patients in Cohort A underwent Cytosponge, using the already collected data will help minimize recall bias. Therefore, Cohort A subjects will only have IES collected for TNE procedure and EGD during this current proposed study.

7.4.2 Procedure Preference and Acceptability Questionnaire

The procedure preference and acceptability questionnaire will be completed with the subject during the follow-up phone call. This assessment collects subject preference for the Cytosponge vs. traditional upper endoscopy vs. TNE, as well as willingness to undergo the procedure again.

7.5 Study Exit

Study participation is complete when the participant has completed the follow-up phone call.

8 RISK AND BENEFIT ASSESSMENT

8.1 Assessment of Safety

All endoscopies and standard of care biopsies referenced in this protocol are consistent with current standard of care, so subjects would be receiving these endoscopies regardless of participation in the study. Therefore, risks related to endoscopy procedures should be reviewed as part of the subject's

clinical care. However, subjects should be reminded of endoscopy risks as part of the consent process for the study. The endoscopy is a well-established procedure with a very low rate of complications. Subjects may experience mild discomfort due to gagging while the tube is passed down the throat. Subjects may also experience mild sore throat, chest pain or discomfort, abdominal pain, or discomfort, or painful or difficult swallowing following the procedure. Medicines may ease these problems. Rare risks from an endoscopy include bleeding and infection. There is a very small risk (about 3 in 10,000) of esophageal perforation that could require surgery to repair and a similarly small risk (8 in 10,000) of aspiration that could cause pneumonia. If clinical biopsies are taken, there is a very small risk of perforation or significant bleeding that would require a blood transfusion or other measures to stop the bleeding. Subjects could also have an adverse reaction to the anesthetic or medication used. These reactions may require treatment. There may be inflammation of the vein through which medication is given. If subjects have asthma, they may have an increased risk for problems with the anesthesia. An adverse reaction to the medications used for the endoscopy can include difficulty breathing, respiratory depression, hypotension, bradycardia, excessive sweating, spasms in the larynx, or an allergic reaction, such as hives and itching or anaphylaxis. These risks are indicative of the procedure itself and are not added risk of participating in the study.

The Seattle biopsy protocol is used for standard of care (SOC) which includes taking four (4) quadrant biopsies every one to two centimeters throughout the area of interest.

Serious risk of endoscopic biopsies is very uncommon in subjects without bleeding disorders and in those who do not regularly take blood thinning medications (such as aspirin, nonsteroidal anti-inflammatory medications, Coumadin (warfarin), Plavix, Lovenox, heparin, and low molecular weight heparin). This is because the biopsies are very small (2-3 mm) and are obtained with blunt tipped forceps under direct vision of the doctor performing the endoscopy. Possible serious complications include excess bleeding from the biopsy sites causing the blood pressure to drop and/or the need for blood transfusion or esophageal perforation (tear) due to trauma. More common, but not serious, is minor bleeding which requires no treatment or responds to treatment with oral antacids. The risk of bleeding secondary to endoscopic biopsies is less than 1/1,000 and there is an even smaller risk of perforation or infection. When bleeding does occur, adequate medical staff and equipment are on hand to abate any long-term damage that could result from this risk. These participants will often already be undergoing biopsies as part of their standard of care, so the incremental risk is expected to be minimal. These risks are indicative of the procedure itself and are not added risk of participating in the study.

Cytosponge risks: There are several risks associated with the administration of the Cytosponge. These include risk of bleeding or aspiration. In addition, discomfort from either the string when the device is in the stomach, or when the sponge is retracted from the body, or mild soreness or irritation in the throat following the procedure which is common in patients receiving an endoscopy, but the Cytosponge may also cause soreness or irritation in the throat.

To date there have been >1,000 administrations and detachment of the sponge from the string has occurred in less than 1% of cases. Detachment of the sponge from the string could block the intestines. Should the sponge detach from the string, it will be retrieved during the routine care upper endoscopy immediately following administration.

To reduce the likelihood of these risks, Cytosponge administration will occur after an overnight fast, to minimize the possibility of aspiration of any gastric contents. Patients' throats may be sprayed with a numbing agent prior to administration of the sponge to minimize discomfort from the procedure. Every

administered sponge will be assessed post-procedure for signs of fracture or incomplete retrieval of the sponge, and in the unlikely case such incomplete retrieval occurs, the sponge will be retrieved during the routine care endoscopy which is scheduled to immediately follow administration of the sponge. If any potential bleeding is noted due to administration of the sponge, this will also be investigated, and, as necessary, treated during the routine upper endoscopy.

Transnasal Endoscopy (TNE) potential risks share the same risks as a conventional endoscopy (reported above). These include nasal discomfort; gagging (mild); discomfort during insertion; aspiration (drawing matter into the lungs along with the breath); bleeding; epistaxis (nosebleed); sinus infection; choking; nausea; retching or vomiting; anxiety; severe pain. A rare risk includes esophageal perforation (occurring in <0.1% of people, or less than 1 out of 10,000 people) which could possibly require surgery to repair.

The equipment for small-caliber endoscopy is FDA approved, and all study procedures will be carried out with trained and/or licensed qualified staff. In the case of procedural complications, the participating investigators will refer the patient for the appropriate care.

8.2 Patient Confidentiality

There is a risk that subjects' confidential medical information could be compromised because of participation in this study. Precautions will be taken to protect confidential information including assigning each subject a unique identifier for study records and restricting access to research records. In addition, study case report forms (CRFs) will collect minimal protected health information.

There may be uncommon or previously unknown risks. Study participants should be instructed to report any problems to the study team for additional reporting per protocol.

8.3 Minimization of Risk

All efforts will be made to minimize risk to subjects who participate in this clinical study.

- Investigators participating in this study are licensed, experienced, and skilled in endoscopic procedures at their institution.
- Treatment and follow-up are consistent with current medical practice.
- Patients will be closely monitored during the procedure and at regularly scheduled intervals for the duration of the study.
- The protocol clearly defines eligibility criteria to ensure that only the appropriate patients are enrolled.
- Investigators agree to maintain the highest level of confidentiality, including conducting appropriate training for site staff prior to study initiation.

8.4 Potential Benefits

It is not expected for participants to benefit directly from participating in this study. Subjects will receive standard of care (SOC) treatment regardless of study participation. There is, however, the potential for researchers and patients to benefit in the future as a direct result of what is learned from this study.

9 STATISTICAL CONSIDERATIONS

9.1 Statistical Plan & Sample Size Calculation

The acceptability of each screening modality will be assessed with the Impact of Events Scale (IES) scores, and the intrusiveness and avoidance subscales. We plan to recruit 40 subjects for the study.

Since the same subject will undergo treatment with each of the screening modalities, we anticipate that the scores generated will be correlated. We assume each pair of scores will have the same correlation. For the planned analysis, each IES score will be classified as low or high. High score will be defined as total IES score >38 .²⁵ A low score will be defined as a total IES score less than or equal to 38.

To compute power, for each of the three devices we specified the proportion of high scores as well as the correlation between observations within a subject. Estimating that 1% of the subjects undergoing sedated EGD group, 5% of those undergoing Cytosponge,²⁵ and 20% of those undergoing TNE will experience a high IES score, using a correlation of 0.3, and a sample size of 40, we specified a trivariate Binomial distribution. Random data were generated from such a distribution and Fishers Exact Test was computed from the data. This was done 10,000 times. The percentage of the 10,000 trials in which the Fishers Exact Test p-value was less than 0.05 provided our power estimate of 80% for a sample size of 40.

We will compare the median IES score for each modality using Kruskal-Wallis testing as well comparing the proportion of subjects with high IES scores for each modality using Pearson's chi-square testing. For the secondary objectives:

- **Secondary objective 1:** Median VAS score will be compared between the three modalities using Kruskal-Wallis testing
- **Secondary objective 2:** The proportion of subjects willing to repeat each test will be computed.
- **Secondary objective 3:** Subjects' preferred screening modality ranked highest will be measured as proportions. The proportion of the highest ranked screening modality will be computed.
- **Secondary objective 4:** Bivariate and multinomial logistic regression analyses will be used to identify factors such as patient discomfort, sex, and EGD indication influencing screening preference among the three modalities.

Since we are recruiting patients from two separate pathways (described in Section 5.1), we plan to account for the differences by analyzing the two groups separately as well as the entire cohort as a whole to see if there is a statistically significant difference in results between the groups. In addition, we acknowledge that the results may be affected by carryover effect for subjects recruited via Pathway 1, but recruiting via this strategy makes this study feasible, and we will acknowledge this as one of the limitations.

All hypothesis tests that are deemed to be not statistically significant will be reported as being inconclusive.

All statistical estimates of population parameters will be tabulated along with corresponding standard errors, or confidence intervals (CI) to convey levels of precision and imprecision.

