5.1 Study Population

We will recruit adults at least 18 years of age who are presenting for routine clinically indicated upper endoscopy (EGD) at UNC. Since the primary objective is to compare patient acceptance and preference between EGD, Cytosponge, and TNE, patients will have to undergo all three procedures. The ideal study design would have subjects undergo all three procedures the same day. However, this could potentially be cumbersome to the patients. To have Cytosponge testing prior to EGD, patients need to present at their EGD appointment more than 2 hours ahead of time. This is because Cytosponge administration requires patients drinking sips of water to swallow the Cytosponge. Following this, patients must wait at least 2 hours prior to undergoing sedated EGD per standard NPO guidelines. Therefore, in an attempt to decrease individual patient burden, we primarily plan to recruit patients from a prior study conducted by our group (IRB #13-2618) who have already undergone Cytosponge and EGD testing and are returning to have a clinically indicated EGD. A significant proportion of these patients, given that they have a history of BE, will undergo routine EGD for BE surveillance. *Patients recruited through this pathway (Cohort A) will be approached to only undergo TNE right before their clinically indicated EGD.*

If we have difficulty recruiting patients through this path, we will plan to recruit subjects who are presenting for a clinically indicated routine endoscopy and recruit them to undergo Cytosponge and TNE prior to their EGD (Cohort B).

Cohort A: Participants from IRB# 13-2618

- Subjects will undergo: TNE, clinically indicated EGD

Cohort B: Cytosponge-naïve

- Subjects will undergo all procedures: Cytosponge, TNE, clinically indicated EGD

After administration, follow-up procedures for both cohorts are the same. Since subjects from Cohort A have already undergone Cytosponge, data from those administrations will be used for VAS, IES, and adaptability of Cytosponge procedures.

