7.3.1 Cytosponge Administration

The Cytosponge will be supplied by Medtronic. The Cytosponge lifetime/use by date will be confirmed on the product packaging. The device received FDA 510(k) clearance on November 26, 2014 (K142695). The Cytosponge device consists of a spherical 3.0 cm diameter reticulated polyester foam compressed and encapsulated in a standard vegetarian capsule (size 00). An investigator, study coordinator, or other trained and qualified personnel will perform the Cytosponge administration and retrieval. Our clinical staff

will be members of the Center for Esophageal Diseases and Swallowing (CEDAS) and are all well versed in the administration and collection of the Cytosponge, due to previous studies our group has conducted (15-0332; 13-2618).

Subjects will undergo administration of the Cytosponge according to the IFU. Briefly, subjects will be placed in the seated position and will swallow the capsule with 150 – 250 mL of water. Additional water may be used if necessary. The sponge is attached to a length of suture material which passes out through the capsule. The suture is affixed to a retainer card, which is held by the subject or administrator to prevent inadvertent swallowing of the suture. The string is to be held without tension as peristalsis and gravity advance the capsule into the stomach.

The capsule dissolves in the stomach, allowing the sponge to expand to its full size. Seven minutes and 30 seconds to ten minutes after ingestion, the sponge is then withdrawn by gentle traction on the suture, collecting cells from the lining of the esophagus in passing. After retrieval, the string is cut and the retrieved foam sphere containing the cytological specimen is immersed in fixative and stored refrigerated (1° to 12°C [34° to 54°F]).

If a subject fails to swallow the Cytosponge, the subject will be asked to swallow again. Subjects who are willing to try again will be asked to wait 5 minutes before the Cytosponge is presented to them again. Subjects will be able to try up to three times before they are classified as “Cytosponge swallowing failure”. Subjects who are unable to swallow the Cytosponge will continue to participate in the remainder of the study.

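### Section 9.1 expects each subject's three scores to be correlated but plans tests for independent groups; these are conservative and lose power, mainly for the IES and VAS scores

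*Combined protocol and SAP*

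**What the plan says.** Section 5.1 sets up a within-subject comparison: "patients will have to undergo all three procedures". Cohort A swallowed the Cytosponge in an earlier study, and Section 7.4.1 brings in each subject's own result from that study: "For Cohort A subjects, we plan to use existing IES data pertaining to Cytosponge which was collected seven (7) days after Cytosponge administration". Section 9.1 draws the consequence: "Since the same subject will undergo treatment with each of the screening modalities, we anticipate that the scores generated will be correlated". It continues, "We assume each pair of scores will have the same correlation", and sets that correlation at 0.3 in the power simulation.

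The analysis in the same section does not follow from this. For IES: "We will compare the median IES score for each modality using Kruskal-Wallis testing as well comparing the proportion of subjects with high IES scores", with Pearson's chi-square for the proportions. For secondary objective 1: "Median VAS score will be compared between the three modalities using Kruskal-Wallis testing". For the two recruitment pathways: "we plan to account for the differences by analyzing the two groups separately as well as the entire cohort as a whole". No other tests are named for those cohort analyses.

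The document names no matched method (Friedman, Cochran's Q, McNemar, mixed model or GEE) and does not say which pairwise comparisons follow the three-way test. Some triples may also be incomplete, because Section 7.3.1 says: "Subjects who are unable to swallow the Cytosponge will continue to participate in the remainder of the study".

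**The concern.** Kruskal-Wallis and Pearson's chi-square treat the 40 × 3 = 120 observations as three separate groups of 40 people. The differences between subjects then stay in the error term, although the design allows them to be removed. With positive within-subject correlation the reference distribution is too wide, so the true type I error falls below 5% and real differences are missed more often.

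IES acceptability is the primary objective and VAS comfort is secondary objective 1, so the affected tests are central to the study. The same tests would presumably be used in the separate cohort analyses, where the samples are smaller. If the mismatch is noticed only after the data are in, any switch to a paired test will be post hoc.

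**Working it through.** **Inputs from Section 9.1.** 40 subjects; high-IES rates of 1% (EGD), 5% (Cytosponge) and 20% (TNE); correlation 0.3; alpha 0.05; Fisher's exact test in the power simulation; stated power 80%.

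**Assumptions not in the documents.** The size of any shift in the scores, their correlation (0.3 is stated only for the high/low simulation), the split between cohorts, and the number without a Cytosponge score. Power was simulated with 10,000 trials per setting, so the Monte Carlo standard error is at most sqrt(0.25/10,000) = 0.5 points.

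**Step 1: the plan's own figure.** Correlated high/low data were generated by thresholding a trivariate normal with correlation 0.3. The 3×2 Fisher test then has 80% to 82% power, so the stated 80% is reproduced. The 0.3 has to be read on the latent scale. Between rates of 1% and 20% the largest possible binary correlation is sqrt(0.01 × 0.80 / (0.20 × 0.99)) = 0.20.

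**Step 2: type I error of Kruskal-Wallis.** With a common correlation ρ between the ranks, the variance of differences in mean rank shrinks by the factor (1 − ρ). The large-sample rejection rate is therefore P(χ²₂ > 5.99/(1 − ρ)) = exp(−2.996/(1 − ρ)).

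| ρ | Formula | Simulated, n = 40 |
|---|---|---|
| 0.1 | exp(−2.996/0.9) = 3.6% | 3.4–3.8% |
| 0.3 | exp(−2.996/0.7) = 1.4% | 1.5–1.6% |
| 0.5 | exp(−2.996/0.5) = 0.25% | 0.3–0.4% |

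Friedman and repeated-measures ANOVA on ranks stay close to 5%.

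**Step 3: power for the scores.** One modality is 0.5 SD worse (assumed); entries are percentages.

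| Setting | Kruskal-Wallis | Friedman | ANOVA on ranks |
|---|---|---|---|
| n = 40, correlation 0.1 | 59 | 52 | 64 |
| n = 40, correlation 0.3 | 59 | 63 | 75 |
| n = 40, correlation 0.5 | 58 | 78 | 87 |
| n = 40, about 69% of scores at zero, latent 0.3 | 46 | 54 | 58 |
| n = 40, Cytosponge 0.1 with the others, EGD–TNE 0.3 | 60 | 58 | 69 |
| n = 40, 4 without Cytosponge, 0.3 (paired tests on complete triples) | 58 | 59 | 70 |
| n = 20, correlation 0.3 | 26 | 36 | 43 |
| n = 20, correlation 0.5 | 22 | 47 | 55 |

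Across other assumed patterns, with largest shifts of 0.4 to 0.6 SD and including skewed scores with a floor, Kruskal-Wallis loses 13 to 18 points to ANOVA on ranks at 0.3 and 25 to 37 points at 0.5.

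**Step 4: high/low IES, n = 40.** With equal rates, Pearson's test rejects 2.5–3.1% of the time at latent correlation 0.3 and 1.3–1.6% at binary correlation 0.3. Asymptotic Cochran's Q rejects 3.7–5.2%. Power:

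| Rates; latent correlation | Pearson | Cochran's Q, asymptotic | Cochran's Q, exact |
|---|---|---|---|
| 1/5/20%; 0.3 | 83 | 86 | 82 |
| 1/5/20%; 0.7 | 85 | 94 | 89 |
| 1/5/15%; 0.3 | 58 | 64 | 55 |

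High scores are rare, which limits the correlation that the binary outcome can carry and so the power that pairing can recover.

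**The case against.** The error is in the safe direction, and the one endpoint with a power calculation hardly suffers. The 80% came from correlated data and an unpaired test, so it already contains the loss. Section 9.1 also says that non-significant tests will be called inconclusive, which guards against reading a missed difference as equivalence.

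For the scores, the 0.5 SD shift is the reviewer's assumption. Suppose instead that the 1%, 5% and 20% rates are read as shifts of a normal score with common variance. The normal quantiles 2.326, 1.645 and 0.842 give shifts of 0, 2.326 − 1.645 = 0.68 and 2.326 − 0.842 = 1.48 SD. At n = 40 all three score tests then have about 100% power. Recruitment is also meant to come mainly from Cohort A, so an even split is not the expected case, and correlations with the earlier Cytosponge score may be low. In that setting Friedman does no better than Kruskal-Wallis (58% against 60%).

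Most of this stands, and it limits the harm: the loss applies to effects smaller than the planned rates imply, to stronger correlation and to small cohorts. It does not rescue the choice of test. Calling a result inconclusive does not restore lost power, the plan gives no power for the scores, and ANOVA on ranks still leads in the low-correlation case (69% against 60%). The weakness of Friedman bears on which paired test to choose; it gives no reason to ignore the pairing.

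**Conclusion.** The concern holds. The tests named for the primary objective and for VAS assume an independence that Section 9.1 itself denies, and nothing elsewhere in the document corrects this. With positive correlation they are conservative, so a significant result can be trusted, and per-modality standard errors and confidence intervals are unaffected. This direction depends on positive correlation, as the plan assumes; negative correlation would reverse it.

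The cost is power. At correlation 0.3 and an assumed 0.5 SD shift it is 75 − 59 = 16 points for the scores against ANOVA on ranks, and 43 − 26 = 17 points in a cohort of 20. For high/low IES at the planned rates it is about 3 points, and the stated 80% stands. The score figures rest on assumed shifts and correlations and would be negligible for very large differences. The tests should still be corrected before analysis, because they are wrong for the design as written and the correction is cheap.

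**What to change.** In Section 9.1:

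1. For IES total, its subscales and VAS, replace Kruskal-Wallis with a within-subject test. Preferably use repeated-measures ANOVA on ranks with the Greenhouse-Geisser correction (at n = 40 and correlation 0.3 the correction lowers power only from 75.2% to 74.6%), or a within-subject permutation test. Friedman is simpler but gains little at 0.3 and loses power near 0.1.
2. For the high-IES proportion, replace Pearson's chi-square with Cochran's Q and its asymptotic p-value. The exact version gains nothing at latent correlation 0.3.
3. If the three-way test is significant, make the three paired comparisons (Wilcoxon signed-rank for scores, exact McNemar for proportions), each at 0.05. With exactly three modalities this is a closed procedure and needs no further adjustment. Report between-modality differences with paired confidence intervals.
4. For incomplete triples, add a mixed model on ranks for the scores, and GEE or available pairs for high/low IES.
5. Restate the power for the chosen test, and say on which scale the correlation of 0.3 applies.

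The cost is wording in Section 9.1 and one rerun of the power simulation, with the same data and standard software. The drawback is slightly more analysis work: the simple paired tests need complete triples, which is why item 4 is included.
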